10.7 Data Management

A quality control (QC) of data will be performed to ensure that data entry and verification have been performed correctly in accordance to pre-defined instructions. The QC will be performed as described in the Data Management Plan (DMP). The QC will be performed before data is declared clean.

11 STUDY MANAGEMENT

11.1 Study time table - End of study

The study is planned in two steps geographically (see 5.4). The first inclusion phase will start in November 2016 in Lund. Last participant in Lund will end medication in May 2017 and will do the final examinations in November 2017. In the overlapping second phase we will start inclusion at Södersjukhuset, Stockholm, by November 2016 and end the study by May 2018.

11.2 Insurance/indemnity

All participants are covered from accidents in connection with the trial by the Patient Injury Act insurance (Patientförsäkringslagen) and from injuries caused by study drug by the Swedish Pharmaceutical Drug Insurance.

The Sponsor agrees to indemnify (legal and financial coverage) and hold the Investigator free of harm from any claim, whether based on legal principles or on generally accepted liability standards within the pharmaceutical industry, made against him by reason of personal injury, including death, to any person arising out of or connected with the performance of the study to the extent that the injury is not caused by:

- 1) Failure by the Investigator to adhere to the terms of the Protocol;
- 2) Failure by the Investigator to comply with any applicable governmental regulations;
- 3) Malpractice, negligence or wilful malfeasance by the Investigator.

The Investigator agrees to notify the Karisma study personnel whenever he/she becomes aware of a claim or action, and to co-operate with and to authorise Karisma study personnel to carry out sole management of such claim or action.

The Sponsor's responsibility is covered by LIF Läkemedelsförsäkring via an association agreement with Kammarkollegiet. The insurance covers Karisma II liability under law and

generally accepted liability standards within the pharmaceutical industry towards any third parties, including participating women, as Sponsor of the study.

11.3 Study agreements

The Principal Investigator at the investigational site must comply with all the terms, conditions, and obligations of the Clinical Study Agreement (CTA) for this study.

11.4 Criteria for termination of the study

The Karisma II study personnel reserves the right to discontinue the study at any time, but intends only to exercise this right for valid scientific or administrative reasons.

After such a decision, the Investigator must contact all participating women within 2 weeks and inform the women as well as perform relevant assessments, preferably according to the scheme for the final assessments. All delivered and unused study products and other study materials must be returned and all eCRFs completed as far as possible.

11.5 Reporting of results and publication policy

A clinical study report, in compliance with ICH E3; Guideline for Industry, will be prepared by the Karisma study personnel, describing the conduct of the study, the statistical analysis performed and the obtained results.

The data generated by this study are considered confidential information and the property of the Karisma Study. Said confidential information may be published only in collaboration with the Karisma study leadership. The Karisma study leadership reserves the right to review and comment on the proposed publication prior to being submitted and/or published.

11.6 Record retention

The Investigator must arrange for retention at the investigational site of a list of the women and their identifying code, subject files and other study documents. The archiving period must be adapted to regulations in force but should not be shorter than ten years after the termination of the study and the presentation of the final report.

It is the responsibility of the Karisma study personnel to inform the Investigator/institution as to when these documents no longer need to be retained

12.2 Emergency unblinding for safety reason

The randomization code (emergency envelopes) are held by Apoteket in Lund. In case of a rare emergency where, in the opinion of the Investigator, discontinuation of the study treatment is not sufficient and the study treatment must be unblinded in order to evaluate further course of action, the Investigator should contact Apoteket Lund (Phone numbers and routines are to be found in the Study Site File) to initiate patient unblinding. In the event the blind is broken, the sponsor should be informed as soon as possible. The date, time, and reason for unblinding must be documented in the appropriate section of the eCRF, and in the source document.

Information about the treatment assignment must be restricted to designated study site staff who are providing immediate care to the patient. Any documentation of the treatment assignment must be maintained separately (i.e. in a secured file). The information must not be included in the patient's source files to ensure the treatment assignment will remain blinded to the monitor and other study personnel not involved with the patient's immediate care.

12.3 Procedures in case of medical emergency

The Investigator is responsible for ensuring that there are procedures and expertise available to cope with medical emergencies during the study. The study is performed at the hospitals Södersjukhuset and Skånes Universitetssjukhus Lund, and any acute medical illness should be dealt with at the hospital.

12.4 Procedure in case of overdose

Overdosing tamoxifen may on theoretical grounds increase the pharmacological side effects of the drug. Any study participant with a suspected or confirmed overdose of tamoxifen should contact the Swedish Poison Information Center.

14 APPENDIXES

- 14.1 Signature pages
- 14.2 Questionnaire
- 14.3 Schedule of events
- 14.4 Additional translational protocol: Biopsy Karisma II
- 14.5 Participant Card

Appendix 14.2; Questionnaires

Questionnaires sent to MPA and IRB are in Swedish and therefore removed from Clinical Trial version of protocol

Appendix 14.3

Schedule of events Karisma II

Schedule of events Karisina II														
	Mx Screening	Baseline						End of treatment						End of study
Events								7						
Month		0	1	2	3	4	5	6	7	8	9	10	11	_12_
Selection of eligible study participants and														
invitation	~													
Mammography within screeningprogram	~													
Mammography for density measure								~						~
Visit at Karma Study centre		'						~						~
Screening for inclusion (inclusion and														
exclusion criterias checked)		/												
Informed consent signed		/												
Blood pressure		/												
Randomization		~												
Blood sampling		/						>						
Biometrics; Length, weight, waist		/						~						~
Pregnancy test (if applicable)		/												
Biopsy (optional)		~						~						
Interview (optional)		~						~						~
IMP administration		/												
Drug acountability check								~						
Karma Baseline questionnaire		~												
Karisma Baseline questionnaire		~												
Follow up questionnaire (sideeffects,														
compliance, concomitant medication)			~		~			~						~
AE-reporting (spontanously)		day2	~	~	~	~	~	~	~	~	~	~	~	~
Check screen mx for exclusion (code 3,4 or 5)	day2												

Appendix 15.4

Additional translational study Protocol: Biopsy Karisma II

1. Objective

Relate changes in breast tissue to different tamoxifen doses and placebo

2. Endpoint

Breast tissue changes between baseline and 6 months of tamoxifen treatment

3. Rational

The molecular basis for the tamoxifen-induced changes in breast density is sparsely understood. Consequently, a secondary aim in the Karisma trial is to investigate changes in tissue markers by comparing breast tissue biopsies sampled prior to and after six months of treatment with different doses of tamoxifen or placebo.

Mammographic density is the white part of the mammogram and consist of glandular and connective tissue. The black, non-radiolucent part is fat. The more glandular and connective tissues, the whiter the breast, and thus; the higher the risk of breast cancer [1]. Factors that influence risk of breast cancer are known to influence density. Hormone replacement therapy increases density and risk of breast cancer, while tamoxifen has the opposite effect [2].

4. Design

Donation of breast biopsies is optional and not a criteria to participate in Karisma II. All Karisma II participants will be invited to donate a biopsy upon study entry. Based on the recruitment frequency of a previous study with breast biopsies conducted within the Karma project, we anticipate that approximately 10% of the Karisma II participants will donate biopsies. Breast biopsies will be collected at study baseline and at month 6 (end of treatment).

5. Investigational plan

- 5.1. Procedure at baseline
 - 5.1.1. Women have to meet inclusion and not fulfil exclusion criteria of the Karisma II study. Women are informed about the study and accompanying procedures by the investigator. If consenting women are invited for breast biopsy.
 - 5.1.2. Only participants with a negative mammogram, defined as BI-RADS score 1 or 2, at baseline are excluded from the study.
 - 5.1.3. The responsible mammography physician performs an ultrasound-led breast biopsy, guided by the mammogram, in the densest part of the left breast under local anaesthesia.
 - 5.1.4. Four core needle biopsies will be extracted from one single incision site. Two cores will be formalin-fixed and paraffin embedded (FFPE) and two cores will be freshly frozen. All four biopsies will be biobanked.
 - 5.1.4.1. Biopsy #1 is the "clinical" FFPE biopsy
 - 5.1.4.2. Biopsy #2 is the "research" FFPE biopsy

- 5.1.4.2.1. The biopsies for FFPE will be sent to Histocenter, Gothenburg, for preparation. HE-stained slides will be sent to the Department of Pathology, Skåne University Hospital, Lund or the South General Hospital, Stockholm, for clinical evaluation. In case of pathological histopathology, participants will be referred for routine clinical work up by the responsible Karisma physician. Diagnostic HE-stained slides will be stored at the relevant Department of Pathology, whereas remaining biopsies will be stored at the Karolinska Institutet Biobank.
- 5.1.4.2.2. Biopsy #3 and #4 are the fresh frozen biopsies for research. Biopsies will be stored at the Karolinska Institutet Biobank.
- 5.1.5. For Biopsy procedure details see SOP Biopsy Karisma II.
- 5.2. Procedure at month 6 (end of treatments)

Procedure according to 5.1.3 to 5.1.4.3.

The procedure at 6 month will follow the schedule of Karisma II and the mammography will not be part of the ordinary screening program.

6. Possible side effects

Breast biopsy is a routine procedure frequently used in clinical practice. The physicians performing the biopsies are all experienced medical professionals. Furthermore, the Karisma II participants are healthy women. The risk of side effects is thus relatively low. The most commonly associated side effects are tenderness at the incision site, contusion and bleeding. Clinical routines apply to deal with these issues.

7. References

Clinical Study Protocol: Karisma II

Appendix 15.5

Participant Card (in Swedish, therefore removed from Clinical Trial version)

### Revision history

Version	Date	Reason for change
0.3	October 17, 2016	First draft
0.4	October 25, 2016	Split of primary analysis

## 1 Preface

This Statistical Analysis Plan (SAP) describes the planned analyses for *Karisma II: A randomized, double blinded, six-armed placebo controlled study to investigate optimal dose of tamoxifen with the most favourable side effect spectra and with mammographic density reduction non-inferior to that of 20 mg tamoxifen*, EudraCT number 2016-000882-22.

The planned analyses identified in this SAP will be included in future manuscripts. Exploratory analyses not necessarily identified in this SAP may be performed to support planned analyses. Any post-hoc exploratory or unplanned analyses not specified in this SAP will be identified as such in manuscripts for publication.

This SAP was written by a statistician and investigators who were blinded to treatment allocation and treatment-related study results and will remain so until the central database is locked and the final data are extracted for analysis. To ensure blinding, treatment allocations are stored in a separate location accessible only by an un-blinded statistician.

## 2 Abbreviations

Abbreviation	Explanation
SAP	Statistical analysis plan
ITT	Intention to treat
PP	Per protocol
MP	Multiple imputation

## 3 Background

For more than 40 years, 20 mg of tamoxifen has been used in breast cancer patients to reduce the risk of recurrence. It has also been shown that 20 mg of tamoxifen reduces the risk of breast cancer (by 40-60%) in healthy women but that the treatment comes with side effects. The side effects are probably one reason to that tamoxifen is not used in the preventive setting despite the substantial risk reducing effect. The aim of the Karisma II study is to identify the lowest tamoxifen dose that could be used for primary preventive purposes, with a hypothesis that a lower dose will reduce the side effects.

Mammographic density is the white part of the mammogram and consist of glandular and connective tissue. The black, non-radiolucent part is fat.

The more glandular and more connective tissues, the whiter the breast, and the higher the risk of breast cancer [1]. Factors that influence risk of breast cancer are known to influence density. Hormone replacement therapy increases density and risk of breast cancer, while tamoxifen has the opposite effect. The molecular basis for the tamoxifen-induced changes in breast density is sparsely understood.

There are three studies that used mammographic density change during one year as a proxy for tamoxifen effect [2–4]. Two projects studied the association between mammographic density change in patients and prognosis and one study looked at density change among perfectly healthy women and risk of breast cancer. All three studies came to the same result, approximately half of the treated participants respond to the therapy by a significant reduction in mammographic density after one year. Those that respond with a decreased mammographic density had a lower risk of breast cancer recurrence and a lower risk of breast cancer.

The conclusion is that change in mammographic density is a very good marker of Tamoxifen therapy response.

## 4 Design

This is a dose determination study aiming to identify the optimal tamoxifen dose for reducing the risk of breast cancer. Instead of following a very large number of women, for many years, treated with different doses of tamoxifen and see if they develop breast cancer, we will include 1440 healthy women participating in the mammographic screening program at two Mammography units (Unilabs mammography, Lund and Södersjukhuset Breast Centre, Stockholm) and measure their change in mammographic density. We will test if 1 mg, 2.5 mg, 5 mg and 10 mg reduce the mammographic density to the same extent as 20 mg. In summary Karisma II will be a randomized, double-blinded, six-armed placebo controlled study to identify the dose of tamoxifen with the most favourable side effect spectra and with a density reduction non-inferior to 20 mg tamoxifen.

Secondary aims of the Karisma II trial are to investigate changes in tissue markers by comparing breast tissue biopsies sampled prior to and after six months of treatment with tamoxifen or placebo, as well as relate levels of tamoxifen metabolites, proteins, lipids and hormones in blood and changes in breast tissue to tamoxifen doses. Moreover, we will study genetic polymorphism in germline DNA and their association to the other endpoints.

[figure not shown]

Figure 1: Overall study design.

#### 4.1 Study population

The study will include healthy women that participate in the mammographic screening program at Södersjukhuset, Stockholm and at Skånes Universitetssjukhus, Lund, and have a negative screening mammogram. We will not include breast cancer patients as they receive a variety of drugs that might influence mammographic density. We are excluding women with no measurable density (< XXX \*\*\* according to the Stratus breast density measurement method \*\*\* this is 4.5% or more by Volpara according to the protocol (p. 17), is this still the way it should be done?). This is because measurable density at study start is a prerequisite for being able to see reduction of mammographic density over time. We are not selecting women based on risk of breast cancer since we currently lack a reliable risk prediction model for Swedish standards.

## 4.2 Study period

Karisma I was a proof of concept study preceding Karisma II. The main reason we conducted the Karisma I study was to investigate time to density change. Radiologists tell us that the time to density change is most probably much shorter than one year, probably only a couple of months. However, the issue of time to density change during tamoxifen therapy has never been addressed.

The results from Karisma I show that, regardless of dose, density decreases within 6 months by about 50% for one quarter of the participants, about 20% for another quarter and not at all for the other participants. This result implicates that tamoxifen intake during 6 months gives a measurable density change of responders; therefore, the treatment period in Karisma II are set to 6 months. From a clinical point of view and for coming study (Karisma III) we will investigate the state of density change and decline of side effects 6 months after tamoxifen cessation in relation to doses.

## 5 Endpoints

### 5.1 Primary objective

Identify the minimal dose of tamoxifen that is non-inferior in its ability to reduce mammographic density compared with 20 mg tamoxifen.

### 5.2 Primary endpoint

Change in mammographic density. In particular, we will test for noninferiority in the proportion of women in the intervention arms (placebo, 1 mg, 2.5 mg, 5 mg, 10 mg) who have a density reduction as great as or greater (after 6 months) than the median density reduction in the 20 mg arm (see Section 6.3).

### 5.3 Secondary objectives

Assess the drop-out level and the level of side effects in the intervention arms compared to the 20 mg arm.

### 5.4 Secondary endpoint

Drop-out rate. We will test for differences in the proportion of drop-outs after 6 months in the intervention arms compared to the 20 mg arm.

## 5.5 Tertiary objectives

Relate levels of tamoxifen metabolites, proteins, lipids and hormones in blood and changes in breast tissue [\*\*\* according to what measure] to tamoxifen doses. Measure genetic polymorphism in germline DNA and relate it to the other secondary objectives. Measure mammographic density and levels of side effects 6 months after tamoxifen cessation in relation to tamoxifen dose. Study associations between dose of tamoxifen, polymorphisms in CYP2D6 and blood levels of endoxifen. Quantify the level of side effects (according to the FACT-ES instrument) and compliance of medicine intake (Morisky scale).

## 5.6 Tertiary endpoints

Levels of tamoxifen metabolites (e.g. endoxifen), proteins [\*\*\* which?], lipids [\*\*\* which?] and hormones [\*\*\* which?] in blood. Breast tissue changes. Genetic polymorphism in germline DNA, in particular CYP2D6. Mammographic density and levels of side effects 6 months after tamoxifen cessation. Side effects (according to the FACT-ES instrument) and compliance of medicine intake (Morisky scale).

# 6 Statistical methods

All analyses will be performed after the study is completed and the database is released. All statistics, including tables, figures and listings, will be performed using SAS, Version 9.3, or R, Version 3.x.

## 6.1 Populations

The intention to treat (ITT) population consists of all women who were randomized and had eligible measure at baseline and at least one eligible measure post baseline. The Per Protocol (PP) Population consists of all women in the ITT population who remained in the study for at least 6 months (the time period during which Tamoxifen is administered) in the study and who had no significant protocol violations (compliance of study drug intake is defined as at least 80% of the prescribed numbers of tablets should be used during time of treatment). The analyses will be preformed on both ITT and PP, however the primary analyses will be carried out on an ITT basis. ITT analysis will likely bias the results toward equivalence for the primary efficacy endpoint compared to if all participants completed the

study (assuming that non-compliance is dose dependant). The per-protocol analysis, on the other hand, excludes data from patients with major protocol violations and may bias the results in either direction. We will therefore analyse the primary endpoint using both intention-to-treat and per-protocol approaches.

Since we expect around 30% dropout rate, we will also create a dataset where missing data is imputed; the multiple imputation (MP) population (see Section 6.9 for details).

## 6.2 Demographics and baseline data

All data will be presented using descriptive statistics. Results will be presented in total, by treatment group, age and menopausal status. Continuous variables will be summarized using number of women, mean, standard deviation, median, minimum and maximum. Categorical variables will be summarized using the number and percentage of women.

## 6.3 Primary analysis: Proportion of responders (efficacy)

The results of both papers [2] and [3] showed that a threshold value in mammographic density decrease needs to be exceeded in order for a woman to experience the beneficial effect of tamoxifen. This threshold value was different in [2] compared to [3]. A 10% or greater reduction was needed in [2] whereas a 20% reduction was needed in [3], a difference most likely explained by different methods of measuring mammographic density. However, the proportion of women exceeding this threshold was exactly 48% in both studies, implying that approximately 50% of the women experience the beneficial effect of tamoxifen irrespective of the way mammographic density is measured.

In the Karma II study, we will use the Stratus method for measuring breast density, which was not used in either [2] or [3]. With support of the results in [2] and [3], we define the response threshold to be the median decrease in mammographic density of women in the 20 mg tamoxifen arm (this definition ensures that the same proportion of women exceeds the threshold as observed in previous studies). Further, we define a responder to be a woman whose mammographic density decrease between baseline and 6 months exceeds the response threshold.

The primary efficacy endpoint is the proportion of responders (women with a reduction of mammographic density, from baseline to 6 months). We will test for non-inferiority with respect to the primary efficacy endpoint for

groups of women treated with placebo, 1, 2.5, 5, and 10 mg compared to the group of women treated with 20 mg tamoxifen. We will use Fisher's exact test with an  $p$ -value of less than 0.05 (corrected for multiple testing, see Section 6.7) as a threshold to declare statistical significance. The non-inferiority margin is defined to be 16.7 percentage points; that is, we define non-inferiority to mean that the fraction of responders is not less than one third of the treated individuals (50% minus 16.7% = 33.3%). The null hypothesis is thus that the proportion of responders in women treated with placebo, 1, 2.5, 5, and 10 mg is 16.7 percentage points less than those women treated with 20 mg tamoxifen (i.e. the fraction of responders is less than one third). For rejection of the null hypothesis, the lower end of the confidence interval needs to be higher than -16.7%. For this to hold, the point estimate of an intervention arm can not be more than 5 percentage points lower than the percent responders in the 20 mg arm.

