This is a dose determination study aiming to identify the optimal tamoxifen dose for reducing the risk of breast cancer. Instead of following a very large number of women, for many years, treated with different doses of tamoxifen and see if they develop breast cancer, we will include 1,440 healthy women participating in the mammographic screening program at two Mammography units (Unilabs mammography, Lund and Södersjukhuset Breast Centre, Stockholm) and measure their change in mammographic density. The change in mammographic density is a very good marker of therapy response. We will test if 1 mg, 2.5 mg, 5 mg and 10 mg reduce the mammographic density to the same extent as 20 mg. In summary Karisma II will be a randomized, double-blinded, six-armed placebo controlled study to identify the dose of tamoxifen with the most favourable side effect spectra and with a density reduction non-inferior to 20 mg tamoxifen.

The Karisma II study will be run in accordance with the ICH GCP guidelines, the principals of which have their origins in the Helsinki 2000 Declaration.

Karisma III

When the optimal tamoxifen dose has been identified in the Karisma II study, we intend to test this dose in women at high risk of breast cancer and study long-term effect of breast cancer incidence. In this phase we plan to include 8,000 women. A separate application will be sent for Karisma III.

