## 6.6 Sample size

Since we have five intervention arms and since we do the primary analysis on a "per arm basis", we have five chances to show noninferiority of the primary endpoint and we therefore need to correct for multiple testing. Standard methods for correcting for multiple testing (according to the methods by Bonferroni or Holm) are too conservative in this context, since they

rely on an assumption of independence between the tests whereas the tests here are clearly correlated. We will instead use the resampling based step-down method suggested by Romano, Shaikh, and Wolf [6], which seamlessly handles correlated tests (see also Section 6.7). The correlation structure of the tests is unknown and we therefore assume that the multiplicativity leads to that the  $\alpha$  decreases from 0.05 to 0.03 in order to declare a significant results (correction by Bonferroni would lead to an  $\alpha$  of 0.01).

With 168 participants in each study arm, the lower limit of the observed one-sided 98.5% confidence limit for the difference will be expected to exceed the non-inferiority margin 16.7 percentage points with a 80% power, assuming that the expected difference in responders between two arms is 0 and the proportion responders in the 20 mg tamoxifen group is 50%. With an estimated 30% drop-out rate, 240 patients in each group need to be randomized.

The trial is powered for the primary analysis. However, we here also briefly investigate the power for showing *both* noninferiority with respect to the primary endpoint and superiority with respect to the secondary endpoint. With 240 participants randomized to each study arm, we have 79% power to show both noninferiority with respect to the primary endpoint and superiority with respect to the secondary endpoint assuming that the proportion of drop outs is reduced by two thirds (from 30% to 10%) and 67% power if the proportion of drop outs is reduced by 50% (from 30% to 15%). (For these calculations, we use the same assumptions about the correlation of the tests as for the analysis of primary endpoint.)

The computations are based on the following formula:

$$n = f(\alpha, \beta) \frac{\pi_s(100 - \pi_s) + \pi_e(100 - \pi_e)}{(\pi_s - \pi_e - d)^2},$$

where  $\pi_s$  and  $\pi_e$  are the true percent 'success' in the standard (20mg) and experimental treatment group respectively, and

$$f(\alpha, \beta) = [\Phi^{-1}(\alpha) + \Phi^{-1}(\beta)]^2,$$

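### Placebo is tested as a fifth candidate for non-inferiority to 20 mg; keeping the family to the four tamoxifen doses would be a near-free gain in power, not a correction of an error rate

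*SAP*

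**What the plan says.** The objective in SAP 5.1 (and Protocol 6.1) is: "Identify the minimal dose of tamoxifen that is non-inferior in its ability to reduce mammographic density compared with 20 mg tamoxifen". Protocol section 4, repeated in SAP 4, describes the comparisons as four: "We will test if 1 mg, 2.5 mg, 5 mg and 10 mg reduce the mammographic density to the same extent as 20 mg".

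The operative sections name five. The primary endpoint in SAP 5.2 and Protocol 6.2 concerns the "proportion of women in the intervention arms (placebo, 1 mg, 2.5 mg, 5 mg, 10 mg"). The primary analysis in SAP 6.3, the Protocol synopsis and Protocol 10.6.2 cover "groups of women treated with placebo, 1, 2.5, 5, and 10 mg compared to the group of women treated with 20 mg tamoxifen".

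SAP 6.6 draws the consequence for multiplicity: "we have five chances to show noninferiority of the primary endpoint and we therefore need to correct for multiple testing". On adjustment it says: "We will instead use the resampling based step-down method". For planning, it assumes that alpha "decreases from 0.05 to 0.03 in order to declare a significant results", and the sample size is based on the "lower limit of the observed one-sided 98.5% confidence limit for the difference". SAP 6.7 repeats the count of five and the 0.03.

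Neither document gives a reason for testing placebo for non-inferiority, or says what a positive placebo result would mean for the choice of dose.

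**The concern.** Only four of the five tests can answer the question that the trial asks. If placebo were declared non-inferior, that would cast doubt on the endpoint or the margin. It would not identify a dose of tamoxifen.

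The fifth test also has a price. In a step-down procedure the critical value depends on how many hypotheses are still unrejected. If tamoxifen lowers density and placebo does not, the placebo hypothesis is hardly ever rejected, so it stays in the set at every step and each of the four doses faces a stricter bound. Because the aim is the lowest adequate dose, power at each individual dose matters, and not only the chance that some dose succeeds.

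**Working it through.** **Inputs from the SAP (6.3, 6.6).** 168 evaluable women per arm, 50% responders in both arms, margin 16.7 points, one-sided alpha 0.015, 80% power, 30% drop-out. Protocol 7.11.5 gives equal allocation.

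**The plan's own figure.** n = (z₀.₉₈₅ + z₀.₈₀)² × (0.25 + 0.25) / 0.167² = (2.170 + 0.842)² × 0.5 / 0.02789 = 162.6, so 163 against the stated 168 (within 3%). Power at 168 is 81.4%. Then 168/0.70 = 240, and 240 × 6 = 1,440, as stated.

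**Power per dose.** SE = √(0.5/168) = 0.0546 and 0.167/SE = 3.061, so power = Φ(3.061 − c), where c is the critical value.

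**First step, five tests against four.** Two arms of equal size and variance that share one comparator have test statistics correlated at 0.5. The Dunnett-type rows use that value. The last row uses the common correlation, about 0.96, at which five tests at a one-sided family level of 2.5% give exactly the SAP's 0.015.

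| Basis | Five tests | Four tests |
|---|---|---|
| Bonferroni, two-sided alpha per test | 0.0100; power 68.6% | 0.0125; power 71.3% |
| Correlation 0.5, family 2.5% one-sided | c = 2.51; 70.9% | c = 2.44; 73.2% |
| Correlation 0.5, family 5% one-sided | c = 2.23; 79.6% | c = 2.16; 81.6% |
| Correlation 0.96, family 2.5% one-sided | alpha 0.0150; 81.4% | alpha 0.0160; 82.0% |

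For 80% power at correlation 0.5 and family 2.5%, the required number per arm goes from 202 to 194. At correlation 0.96 it goes from 163 to 160.

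**Later steps.** Correlation 0.5, family 2.5%. With a placebo that is never rejected, the four doses, taken from strongest to weakest, face one-sided levels of 0.0060, 0.0073, 0.0094 and 0.0135. Without placebo they face 0.0073, 0.0094, 0.0135 and 0.025. The gap is widest for the weakest dose.

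**Step-down simulation.** 400,000 trials, family-wise 2.5% one-sided, 168 per arm. The placebo responder rate is not in the documents. It is assumed to be 20%, and rates of 10% and 30% give the same power for the doses.

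| Doses truly at 50% (others at 33.3%) | Power per such dose, placebo in | Placebo out |
|---|---|---|
| All four | 76.0% | 80.8% |
| Three | 74.1% | 77.0% |
| Two | 72.6% | 74.7% |
| One | 72.7% | 72.6% |

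With all four doses at 50%, the chance of showing all four goes from 54% to 66%. The chance of showing at least one is 94.0% in both cases.

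The last row shows no gain because responder counts are whole numbers. The largest shortfall allowed at the first step is (0.167 − c × SE) × 168, which is 5.04 women for c = 2.51 and 5.68 for c = 2.44. Both round down to five.

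**Error rate.** With three doses at 50% and one on the margin, the marginal dose is passed in about 1.4% of trials with placebo in the family and about 2.5% without. Both respect the 2.5% level.

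**The case against.** **The documents do not really conflict.** Every operative section includes placebo. The four-dose wording is one descriptive sentence, used in both documents, and it does not say that only those doses are tested. This stands: an analyst would run five tests. The mismatch is worth aligning, but it does not make the analysis ambiguous.

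**Placebo is labelled as a dose.** The Protocol synopsis and 7.11.3 list it as 0 mg. A reader might therefore infer that the rule could return 0 mg as the minimal dose. The objective speaks of a dose of tamoxifen, and the result is remote if tamoxifen works: placebo passed in about 0.02% of simulated trials or fewer at an assumed 20% responder rate, and in about 0.5% at 30% with all four doses at 50%.

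**A placebo test is informative.** The pilot compared 10 and 20 mg without placebo, so a placebo that met the margin would show that the endpoint or the margin cannot separate active from inactive treatment. That has value, although the documents do not give it as a reason. It argues for a comparison with placebo, but not for a place in this family. Failing to show placebo non-inferior does not show that 20 mg is better than placebo.

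**The power figures are not those of the planned method.** This also stands. The SAP calls the correlation unknown, and the title of the method paper it cites concerns the false discovery rate, whereas the figures above control the family-wise rate. A false-discovery-rate version at correlation 0.5 gave a similar gap per dose (85.2% to 89.1%). At correlation 0.96 the step-down gap is about 1 point.

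**Nothing is invalid.** Correct. The larger family is conservative, the estimates do not change, and the trial still reaches its stated 80% on its own assumptions.

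**Conclusion.** This is an efficiency improvement. A reader might infer an inflated type I error, an underpowered trial or a contradiction that undermines the primary analysis. The documents support none of these: five tests are stricter than four, the stated power is met on the plan's own inputs, and placebo is included consistently wherever the analysis is specified.

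What holds is that one of the five tests cannot serve the stated objective and takes some power from the four that can. The cost per dose is about 0.7 points at the correlation implied by the SAP's 0.03. At correlation 0.5 it is about 2 points at the first step by the normal approximation, and about 5 points under family-wise step-down if all four doses match 20 mg. It shrinks as fewer doses match 20 mg. The chance of showing at least one dose hardly moves.

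These sizes rest on an assumed correlation, family-wise control and an assumed placebo responder rate. They also treat the 20 mg responder rate as binomial, although the threshold is the observed median of that arm. The exact loss under the planned resampling method cannot be derived from the documents.

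**What to change.** Define the non-inferiority family as 1, 2.5, 5 and 10 mg, each against 20 mg. Run the step-down adjustment over those four tests, and restate the planning alpha for four. Align the Protocol synopsis, 6.2 and 10.6.2 and SAP 5.2, 6.3, 6.6 and 6.7 with Protocol section 4 and SAP 4.

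Keep placebo outside the family as a pre-specified comparison of responder proportions, 20 mg versus placebo, reported as a difference with its confidence interval. State that it is a check of assay sensitivity, and what a small difference would mean for interpreting the dose results.

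The cost is wording and one fewer hypothesis in the resampling code, with no extra participants. Protocol 10.6 has the SAP finalised before database lock, so the change fits the planned process. The small downside is that placebo no longer has a multiplicity-adjusted non-inferiority test; the separate comparison takes its place.
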